### **3.3. Data collection**

During the study, the information will be collected from 3 sources:

- 1. Information collected via telephonic surveys (see Appendix 1);
- 2. Information collected during interviews at the clinical sites (see Appendix 2);

### **3.4. Ethical and legal aspects**

Currently, results of the studies of SARS-CoV-2 infection prevalence in the population have key importance for public health in particular regions as well as at national and international levels. Conduction of such observational population studies is a key objective of scientific and practical medical institutions to be able to inform the society about the current epidemiological situation.

This observational study will involve blood sampling for the antibodies test; this procedure has minimal risks for the health. Participation in the study will not affect medical decisions

in any manner. The nature of participation is completely voluntary. The participants will be informed about the results, but it is not recommended to interpret these results from the point of view of protection from the infection.

This study will be conducted in adherence to applicable local, regional, and national laws and regulations. Non-interventional epidemiological observational studies without investigational drugs are not directly regulated by International Council on Harmonization (ICH) Good Clinical Practice (GCP), but before the start of the study, an ethics committee will perform a review, and the GCP principles will be applied as needed.

This study is being conducted at the territory of the Russian Federation, in accordance to the laws and regulations applicable to epidemiological observational studies. No personal data will be used in data analysis or transferred to the European University at St. Petersburg as well as to laboratories performing the tests.

Participation in the study is completely voluntary and is possible only after the familiarization with the Information Sheet (Appendix 3), study details explanation, and signing correspondent Informed Consent Forms (Appendix 3). The participants can withdraw their consent verbally or in written form at any moment. Withdrawal of consent applies to personal information and results of all tests and procedures which would follow the moment of withdrawal, as well as other personal data. Withdrawal of consent does not apply to already collected and analyzed, anonymized and aggregated data, as such data cannot be identified.

Results of this study cannot be the only reason for making decisions about the epidemics control measures, but they can be used in discussion of such measures.

#### **4. Laboratory diagnostics**

To measure IgG antibodies titer, Abbott Architect SARS-CoV-2 IgG (<https://www.fda.gov/media/137383/download>) assay will be used. According to the manufacturer, the sensitivity of the assay is 100%, and the specificity is 99.6%. With a scientific objective, Coronapass Total Ig assay (Genetico) will also be used, with the sensitivity of 96% and specificity of 100%, according to the manufacturer. Other point-of-care tests can be used to immediately inform participant but not for the research analysis.

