## List of Appendices

**Appendix 1. Questionnaire for telephonic survey.**

**Appendix 2. Medical questionnaire.**

**Appendix 3. SARS-CoV-2 antibody test results.**

**Appendix 4. Participant Information Sheet and Informed Consent Form.**

## **1. Introduction**

Population analysis of infection spreading is one of the key methods of new epidemics control. The World Health Organization has included population serological surveys, which help to visualize the new virus distribution, into a list of essential assessments during the current epidemics, along with the vaccine development and search for effective treatments for severe disease. Such studies help understand real disease spread and a real proportion of fatal outcomes among the patients with a disease and infected persons. Initial studies have shown the presence of immune response to an earlier SARS-CoV-2 infection.

Regarding the SARS-CoV-2 pandemic, the population assessment of immune response is recommended until the year 2024, as currently there is a discussion of a high risk of second and further peaks of new coronavirus epidemics. Initial studies performed in the state of New York have shown that up to 14% state residents and 21.2% of New York City residents had had the infection and had developed antibodies. In the states of Idaho and California, there were not more than 2% of such people.

To evaluate the proportion of people who have had the disease in a whole population (a city, a region, a country), the representativeness of a sample needs a strict approach. The methodology of a serological study is in many aspects similar to a sociological survey but is more complicated due to the use of serological test results. In addition, the population characteristics of these tests, i.e. sensitivity and specificity, are not always well-known. A serological study sample should be representative for the general population (age groups, gender, place of living, mobility during the epidemics).

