#### **5. Statistical analysis**

##### **5.1. Sample**

In this study, a population of a region with the size of  $N$  is being looked at. Assuming that the number of infected ( $K$ ) in the population is distributed binomially and the serological test is ideal, 2-sided 95% Wilson confidence interval for the prevalence ( $p$ ) is:

$p' \pm z_{0,025} \sqrt{\frac{p'(1-p')}{n+4}}$ , where  $p' \equiv \frac{k+2}{n+4}$ , and  $z_{0,025}$  is the critical level of the standard normal distribution. In this case the sample size  $n$ , needed for the sample error to not exceed  $M$ , with a conservative assumption of hypothetical prevalence of 50%, is:  $n > \left(\frac{1,96 \times 0,5}{M}\right)^2 - 4$ . For the sample error to reach 2%, at least 2397 observations are needed.

If we assume that hypothetical prevalence is 10%, the sample size is less than 900 for the sample error of 2%. Taking into account possible attrition at the repetitive tests, it is planned to enroll at least 1000 participants.

During the study, it is planned to test at least 1000 participants with a highly sensitive (Se) and highly specific (Sp) test, to reach the sample error level of 2%. The calculations above are applicable to a cross-sectional study. In a cohort study, there is a problem of the sample attrition. We assume loss of 5% of participants at the repetitive blood sampling. If 1000 participants provide samples at the first visit, there will be 630 tested participants at Week 36.

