### 5.3.1. Primary objective

**Cross-sectional study:** the main objective of this study is to calculate the proportion of participants with the presence of antibodies (taking into account the threshold recommended by manufacturer) in the total number of tested. Crude value will be equal to the proportion of positive-tested persons in the total number of enrolled. Additionally, standardized values and values in age or gender groups will be calculated as well as an adjusted value based on the total population in a region.

**Cohort study:** the main objective of the cohort study is to compare correspondent values of prevalence in different points in time. This comparison will be made using simple tests and models depending on the type of value (rough, standardized, adjusted).

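### No prevalence value listed in the Protocol corrects for assay error, although the Protocol quotes imperfect accuracy for both assays and aims to estimate past infection

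*Protocol*

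**What the plan says.** - **Target.** Section 2.1 sets the pilot objective as the proportion of city residents who have already been infected, judged from serum antibodies.
- **Assay accuracy.** Section 4, on Abbott: "According to the manufacturer, the sensitivity of the assay is 100%, and the specificity is 99.6" (per cent). On Genetico: "with the sensitivity of 96% and specificity of 100%, according to the manufacturer". The Introduction warns that the population characteristics of such tests, "i.e. sensitivity and specificity, are not always well-known".
- **Sample size.** Section 5.1 derives its interval assuming that the number infected "in the population is distributed binomially and the serological test is ideal". It later plans to test "with a highly sensitive (Se) and highly specific (Sp) test", but neither symbol enters a formula.
- **Estimators.** Section 5.3 lists an uncorrected prevalence, a singly imputed one, and two corrected for self-selection (on observed and on unobserved characteristics). Section 5.3.1 counts positives at the manufacturer's cut-off and adds standardised values, age and gender values, and "an adjusted value based on the total population in a region".
- **Which assay.** Section 3.1 names Abbott and Genetico together as the main assays. Section 4 gives Abbott as the assay for measuring IgG and says Genetico is used as well, for a scientific purpose. Neither section says which result defines prevalence.

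**The concern.** The target is past infection, but the estimator is the proportion above a cut-off. The two agree only if the assay makes no errors, and Section 4 says that each assay makes some: false positives for Abbott, false negatives for Genetico. The resulting shift is systematic. It does not shrink with sample size, and an interval that reflects only sampling error does not contain it. The listed corrections for participation and population structure leave it in place.

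At stake are the position of the published prevalence and the true coverage of its 95% interval. Because the two assays err in opposite directions and the defining assay is not fixed, even the sign of the shift is left open.

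**Working it through.** **1. The plan's own figures (Section 5.1, ideal test).**
- At 50% prevalence: n = (1.96 × 0.5 / 0.02)² − 4 = 2397. This matches.
- At 10%: 1.96² × 0.10 × 0.90 / 0.02² = 864. With the Protocol's own interval, centred on (k + 2)/(n + 4), n = 875. Both agree with the stated bound of under 900.

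**2. Inputs for the check.** Sensitivity (Se) and specificity (Sp) come from Section 4: Abbott 1.00 and 0.996, Genetico 0.96 and 1.00. The true prevalences are 10% (planning value, Section 5.1), and 2% and 21.2% (figures cited for other places in the Introduction). The sample is n = 1000.

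**3. Apparent prevalence** = p × Se + (1 − p)(1 − Sp).
- Abbott, 10%: 0.10 + 0.90 × 0.004 = 0.1036
- Genetico, 10%: 0.10 × 0.96 = 0.0960
- Abbott, 2%: 0.02 + 0.98 × 0.004 = 0.0239
- Genetico, 2%: 0.02 × 0.96 = 0.0192
- Abbott, 21.2%: 0.212 + 0.788 × 0.004 = 0.2152
- Genetico, 21.2%: 0.212 × 0.96 = 0.2035

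**4. Coverage of the Section 5.1 interval.** The number positive is binomial with n = 1000 and the apparent prevalence above. Coverage is the summed probability of all counts whose interval contains the true prevalence.

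| True prevalence | Assay | Reads as | Bias (points) | Coverage |
|---|---|---|---|---|
| 2% | Abbott | 2.39% | +0.39 | 82.7% |
| 2% | Genetico | 1.92% | −0.08 | 94.9% |
| 10% | Abbott | 10.36% | +0.36 | 92.8% |
| 10% | Genetico | 9.60% | −0.40 | 93.4% |
| 21.2% | Abbott | 21.52% | +0.32 | 94.3% |
| 21.2% | Genetico | 20.35% | −0.85 | 90.6% |

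With a perfect test the same interval covers 94.7% to 95.2% at these three prevalences, so the shortfall comes from assay error and not from the interval method.

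**5. Effect of correcting.** Rogan-Gladen: corrected = (apparent + Sp − 1)/(Se + Sp − 1).
- An observed 10.0% becomes (0.100 − 0.004)/0.996 = 9.64% for Abbott, or 0.100/0.96 = 10.42% for Genetico.
- Applying the same transformation to the interval limits gives coverage of 95.0% to 95.3% in all six rows, with Se and Sp taken as known.

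**6. Does the planned sample size survive?** The corrected half-width is 1.96 × √(apparent × (1 − apparent)/n)/(Se + Sp − 1). At true 10% and n = 1000:
- Abbott: 1.96 × √(0.1036 × 0.8964/1000)/0.996 = 1.90 points
- Genetico: 1.96 × √(0.096 × 0.904/1000)/0.96 = 1.90 points

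A 2-point half-width needs about 899 (Abbott) or 904 (Genetico) participants, so 1000 suffices.

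**The case against.** **A correction could sit in an unseen statistical analysis plan.** The Protocol does not call its list exhaustive, and the interval method and accuracy range are details such a plan usually holds. That part stands. But the Protocol does not defer here. It names its estimators one by one, including elaborate selection models, and leaves out an error whose inputs it quotes.

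**The perfect-test assumption is stated only for sample size.** This also stands. For the analysis values it follows from the absence of any Se or Sp term. A reader might infer that the adjusted value in Section 5.3.1 is presented as free of assay error. It is not: the text ties it to the regional population and claims nothing about the assay.

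**The size is easy to overstate.** Three stronger readings are not supported:
- The gap between assays at true 10% is 10.36 − 9.60 = 0.76 points, or 38% of the 2-point margin. That is a difference between two assays erring in opposite directions. An estimate from one assay is off by 0.36 or 0.40 points, about a fifth of the margin.
- It is tempting to say the error is worst at low prevalence. That is true only of Abbott's relative error (about +20% at 2%). Genetico's relative error is constant at −4%, and its absolute error grows with prevalence.
- The Protocol cites about 2% for other places and does not predict it for St. Petersburg.

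**Correcting with the manufacturer's figures can make matters worse.** Suppose, as an assumption, that Abbott sensitivity were 85–95% with specificity 99.6%. A true 10% would then read 8.86–9.86%. Correction with the quoted 100% and 99.6% would give 8.49–9.50%, further from the truth. This stands, and it argues against making a single corrected value the headline result.

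**Conclusion.** The point holds as a gap in the listed estimators. Followed as written, Sections 5.3 and 5.3.1 give prevalence values shifted from the stated target by an error that the Protocol quantifies itself. At the 10% planning prevalence the shift is +0.36 or −0.40 points, and coverage falls to about 93%. The worst case among the cited prevalences is Abbott at 2% (coverage about 83%), followed by Genetico at 21.2% (about 91%).

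These sizes assume that the manufacturers' figures are exact, that one assay defines the result, that n = 1000, and that sampling is simple binomial. Selection effects are left out.

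A reader might infer that the sample size is invalid. It is not, since the 2-point target is still met after correction with Se and Sp taken as known. The issue is worth fixing because the fix is cheap, but it does not undermine the design.

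**What to change.** 1. State which assay result defines prevalence, and reconcile Section 3.1, which names both assays, with Section 4.
2. Add to the list in Sections 5.3 and 5.3.1 a Rogan-Gladen corrected value, (apparent + Sp − 1)/(Se + Sp − 1), reported beside the uncorrected value for each assay.
3. Show the corrected value over a stated range of sensitivity and specificity, not at the manufacturers' figures alone. Where validation data allow, carry the uncertainty in both into the 95% interval. The Protocol gives no validation sample sizes, so these would have to be obtained.

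**Cost.** No new participants or samples are needed. Correcting an overall prevalence takes little analysis work; allowing for misclassification inside the selection models would take more and is not required here. Intervals for the corrected value become wider: at 10% and n = 1000, the half-width goes from 1.87 points with the Section 5.1 interval to 1.90 with accuracy taken as known, and further once its uncertainty is included.

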#### **5. Statistical analysis**

##### **5.1. Sample**

In this study, a population of a region with the size of  $N$  is being looked at. Assuming that the number of infected ( $K$ ) in the population is distributed binomially and the serological test is ideal, 2-sided 95% Wilson confidence interval for the prevalence ( $p$ ) is:

$p' \pm z_{0,025} \sqrt{\frac{p'(1-p')}{n+4}}$ , where  $p' \equiv \frac{k+2}{n+4}$ , and  $z_{0,025}$  is the critical level of the standard normal distribution. In this case the sample size  $n$ , needed for the sample error to not exceed  $M$ , with a conservative assumption of hypothetical prevalence of 50%, is:  $n > \left(\frac{1,96 \times 0,5}{M}\right)^2 - 4$ . For the sample error to reach 2%, at least 2397 observations are needed.

If we assume that hypothetical prevalence is 10%, the sample size is less than 900 for the sample error of 2%. Taking into account possible attrition at the repetitive tests, it is planned to enroll at least 1000 participants.

During the study, it is planned to test at least 1000 participants with a highly sensitive (Se) and highly specific (Sp) test, to reach the sample error level of 2%. The calculations above are applicable to a cross-sectional study. In a cohort study, there is a problem of the sample attrition. We assume loss of 5% of participants at the repetitive blood sampling. If 1000 participants provide samples at the first visit, there will be 630 tested participants at Week 36.

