## 5.2. Encouragement design

Even if random sample of potential participants (surveyed persons) is representative, the decision about the participation in the study may bias its results, as it is made (or rejected) by a potential participant. The assumption of ideal participation of all surveyed persons in the testing is unrealistic. The next step would be to assume self-selection based on the observed characteristics of the surveyed. But it is doubtful that during a telephonic interview all observed individual characteristics which may affect the decision about the participation may be identified and quantified. For this reason, the final assessment of the prevalence will be biased. To surpass the issue of non-observable decision about the voluntary participation, the encouragement design will be used in this study.

A randomly selected subgroup of the surveyed will be offered a benefit related to the study participation, free-of-charge taxi to the place of testing. This offer will be made during the interview. Such randomization will permit to assess the proportion of infected in the group of people whose decision to participate in the testing changes depending to this benefit. The prevalence assessed in this manner has higher external validity than the prevalence in the group of people who make the decision without external encouragement.

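### Enrolling 1000 gives a 2-point sampling error at the first visit if prevalence is 10%, but it does not absorb the attrition that Section 5.1 says it allows for: the margin covers about two of nine repeat visits

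*Protocol*

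**What the plan says.** Section 5.1 bases the sample size on a "2-sided 95% Wilson confidence interval for the prevalence", on the assumption that "the serological test is ideal". It starts from the conservative case of 50% prevalence: "For the sample error to reach 2%, at least 2397 observations are needed". It then relaxes the assumption: "If we assume that hypothetical prevalence is 10%, the sample size is less than 900 for the sample error of 2" percent. The enrolment target follows directly: "Taking into account possible attrition at the repetitive tests, it is planned to enroll at least 1000 participants". The next paragraph repeats that at least 1000 will be tested "to reach the sample error level of 2" percent, this time without naming a prevalence.

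The same section adds that the calculation applies to a cross-sectional study and that attrition is a problem for the cohort. With 5% lost at each repeat sampling, 630 will be tested at Week 36. The table in Section 3.1 gives the expected number at all ten visits. Section 5.3.1 makes comparison of prevalence between time points the main objective of the cohort part.

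**The concern.** Attrition does not arise in a single cross-section, so the sentence that sets enrolment at 1000 can only be a statement about the repeat visits. It presents the step from under 900 to 1000 as the allowance for loss. The protocol's own table then shows numbers falling below 900 after Week 8 and reaching 630. No precision is given for those rounds.

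This is the only precision statement in the protocol. A reader would take from it that each round estimates prevalence to within 2 points, and the later rounds are the ones that the cohort objective compares. The figure also depends on the 10% assumption, for which no basis is given, and the second mention of 2% drops that condition.

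**Working it through.** **Inputs.** From Section 5.1: two-sided 95%, z = 1.96; target half-width M = 0.02; prevalence p = 0.50 and p = 0.10; ideal test; 5% loss per repeat visit. From the Section 3.1 table: numbers tested at each visit. From the Introduction: prevalence elsewhere of not more than 2%, 14% and 21.2%.

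**Step 1. Reproduce the plan's figures.** The protocol's formula is n = z²p(1−p)/M² − 4.
- p = 0.50: (1.96 × 0.5/0.02)² − 4 = 2401 − 4 = 2397. Agrees.
- p = 0.10: 1.96² × 0.09/0.02² − 4 = 864.4 − 4 = 860.4, so 861. Agrees with fewer than 900.
- Week 36: 1000 × 0.95⁹ = 630.2. Agrees with 630.

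**Step 2. Check whether the requirement depends on the interval used.** The protocol's interval is centred on p′ = (k+2)/(n+4), but its sample-size formula ignores that shift. The number needed at 10% is 861 by the protocol's formula, 865 by the simple Wald interval, 868 by the Wilson score interval and 875 by the protocol's interval with the shift. All are below 900 and all are above 857.

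**Step 3. Half-width at each visit, at 10% prevalence.** Half-width = 1.96 × √[p′(1−p′)/(n+4)], with p′ = (np+2)/(n+4).
- First visit: p′ = 102/1004 = 0.1016; 1.96 × √(0.1016 × 0.8984/1004) = 0.0187.
- Week 36: p′ = 65/634 = 0.1025; 1.96 × √(0.1025 × 0.8975/634) = 0.0236.

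| Visit | Tested | Half-width at 10% (points) |
|---|---|---|
| First | 1000 | 1.87 |
| Week 4 | 950 | 1.92 |
| Week 8 | 902 | 1.97 |
| Week 12 | 857 | 2.02 |
| Week 16 | 815 | 2.07 |
| Week 20 | 774 | 2.13 |
| Week 24 | 735 | 2.18 |
| Week 28 | 698 | 2.24 |
| Week 32 | 663 | 2.30 |
| Week 36 | 630 | 2.36 |

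Across the four variants in Step 2 the half-width is 2.00 to 2.02 at Week 12 and 2.34 to 2.36 at Week 36. The target is met at the first visit and at two repeat visits (Weeks 4 and 8).

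**Step 4. Largest prevalence at which 2 points still holds.**
- n = 1000: 11.7% to 11.9%, depending on the variant.
- n = 857: 9.8% to 10.0%.
- n = 630: 6.8% to 7.1%.

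**Step 5. Other prevalences cited in the protocol (same interval as Step 3).**

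| Prevalence | First visit (1000) | Week 36 (630) |
|---|---|---|
| 10% | 1.87 | 2.36 |
| 14% | 2.16 | 2.72 |
| 21.2% | 2.53 | 3.19 |

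**Step 6. What an attrition allowance would have required, for scale only.** To keep 865 to 875 results at Week 36: 865/0.6302 = 1,372 and 875/0.6302 = 1,388 at the first visit, against 1000.

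**The case against.** Much of the defence stands. The stated figures (2397, fewer than 900, 630) all reproduce. The 10% is a disclosed assumption, set beside a conservative 50% case, so a reader is told that higher prevalence needs more people. Section 5.1 limits its calculation to the cross-sectional part and discloses the 630. The first-visit crude estimate meets the target, 1000 is a minimum, and the Week 12 excess is trivial. If prevalence is below about 7%, 2 points holds through Week 36. The Introduction supports low values as well as high ones: beside "up to 14% state residents and 21.2% of New York City residents" it cites not more than 2% in two other states.

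The scope sentence still does not rescue the attrition claim. That claim concerns repeat tests, which lie outside the cross-sectional calculation, and disclosing 630 without its precision leaves the claim uncorrected.

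A reader might go further and infer that 2 points is lost for every selection-corrected estimate, since Section 5.2 intends to "assess the proportion of infected in the group of people whose decision to participate in the testing changes depending to this benefit" and such estimates can be much less precise. The documents do not support that as a calculated result. They give no response rate, effect of the taxi offer, allocation ratio or selection correlation. Section 5.3 specifies joint regression models and does not list a simple ratio of between-arm differences. At 10% and n = 1000, a corrected estimate would keep 2 points as long as its variance were inflated by no more than about 1.15. Section 5.3 also promises each value its own 95% interval. What can be said is that the 2 points was derived for a binomial proportion with an ideal test and for nothing else.

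**Conclusion.** The statement that 1000 allows for attrition is wrong on the plan's own formula and table. At the assumed 10% prevalence, the step from under 900 to 1000 covers about two of nine repeat visits. The excess over 2 points is marginal at Week 12 and grows to about 0.35 points at Week 36. At the first visit the 2-point claim is correct at 10% and holds up to about 12%.

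This rests on the protocol's 5% loss per visit, its ideal-test assumption and exactly 1000 at the first visit. More enrolled, less loss or lower prevalence would ease it; higher prevalence would worsen it. It is not a claim that 10% is the wrong planning value, that the sample must be enlarged, or that the corrected estimates have any particular precision. Severity is minor to moderate: the stated precision needs correcting, but neither the design nor the analysis changes.

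**What to change.** Amend Section 5.1 and keep the enrolment target at 1000:

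- Remove the statement that 1000 allows for attrition.
- State that the 2-point error applies to the crude proportion at the first visit, if prevalence is about 12% or lower, and attach that condition to the second mention of 2% as well.
- Give the expected half-width by visit and prevalence. For the first visit and Week 36: about ±1.9 and ±2.4 points at 10%, ±2.2 and ±2.7 at 14%, ±2.5 and ±3.2 at 21%.
- Add one sentence saying that the 2 points was not derived for the selection-corrected estimates, without assigning them a figure.

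The cost is a text change in one section, with no added recruitment and no change to the analysis. The downside is that the stated precision becomes slightly less favourable.
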